## **8.6. Safety Analysis**

All safety analyses will be performed using the safety analysis set.

All safety data collected on or after the date that the study drug was first administered up to the date of the last dose of study drug plus 30 days, unless specified otherwise, will be summarized for subjects in the safety analysis set according to the study drug received.

Data for the pretreatment period and the period post the date of last dose of study drug plus 30 days will be included in data listings for all enrolled subjects.

### **8.6.1. Extent of Exposure**

A subject's extent of exposure to study drug will be generated from the study drug administration page in eCRF. Exposure data will be summarized by treatment.

Duration of exposure to study drug will be expressed as the number of weeks between the first and last dose of the study drug, inclusive, regardless of temporary interruptions in study drug administration and summarized by treatment.

Dosing information for individual subjects will be listed.

### **8.6.2. Adverse Events**

Clinical and laboratory adverse events will be coded using the Medical Dictionary for Regulatory Activities (MedDRA). System Organ Class (SOC), High-Level Group Term (HLGT), High-Level Term (HLT), Preferred Term (PT), and Lower-Level Term (LLT) will be attached to the clinical database.

Events will be summarized on the basis of the date of onset for the event. A treatment-emergent adverse event will be defined as any adverse event with onset date on or after the study drug start date and no later than 30 days after the study drug stop date; or any adverse event leading to study drug discontinuation.

Summaries (number and percentage of subjects) of treatment-emergent adverse events (by SOC, HLT [if applicable], and PT) will be provided by treatment. Additional summaries will include summaries for adverse events by grade, Investigator's assessment of relationship to study drug, and effect on study drug dosing.

On an ongoing basis adverse events will be reviewed for events that might meet the definition of Stage 3 Opportunistic Illnesses in HIV are indicative of an AIDS-Defining Diagnoses. The Gilead medical personnel will review the possible Stage 3 events and approve the events that meet the definition. Those events that do meet the Stage 3 Opportunistic Illnesses definition of an AIDS-Defining Diagnosis will be listed.

A listing of Stage 3 Opportunistic Illnesses in HIV can be found in [Appendix 5](#).

### **8.6.3.        Laboratory Evaluations**

Selected laboratory data (using conventional units) will be summarized using only observed data. Absolute values and changes from baseline at all scheduled visits will be summarized.

Graded laboratory abnormalities will be defined using the grading scheme defined in Grading of laboratory abnormalities attached in [Appendix 4](#).

Incidence of treatment-emergent laboratory abnormalities, defined as values that increase at least 1 toxicity grade from baseline at any time post baseline up to and including the date of last dose of study drug plus 30 days, will be summarized by treatment. If baseline data are missing, then any graded abnormality (i.e., at least a Grade 1) will be considered treatment emergent. The maximum post baseline toxicity grade will be summarized by laboratory parameter.

Laboratory abnormalities that occur before the first dose of study drug or after the last dose of study drug plus 30 days will be included in a data listing.

### **8.6.4.        Other Safety Evaluations**

Vital signs and safety ECG data will be summarized as appropriate.

### **8.7.            Pharmacokinetic Analysis**

For the PK analyses, the pharmacokinetics of GS-9883 may be evaluated using descriptive statistics or population approaches.

TAF and FTC concentrations may be analyzed as applicable.

### **8.8.            Sample Size**

A total of approximately 470 HIV-1 infected subjects, randomized in a 1:1 ratio to 2 treatment groups (approximately 235 subjects per treatment group), achieves at least 87% power to detect a non-inferiority margin of 4% difference in percentage of subjects with HIV-1 RNA  $\geq$  50 copies/mL at Week 48 between the 2 treatment groups. For the sample size and power computation, it is assumed that both treatment groups have 2% of subjects with HIV-1 RNA  $\geq$  50 copies/mL at Week 48 (based on the historical Gilead GEN and STB studies), that the non-inferiority margin is 4%, and that the significance level of the test is at a one-sided 0.025 level.

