**Statistical Methods:**

The primary analysis will consist of a non-inferiority test of switching to GS-9883/F/TAF FDC versus SBR with respect to the proportion of subjects with HIV-1 RNA  $\geq 50$  copies/mL at Week 48 as determined by the US FDA-defined snapshot algorithm. It will be concluded that GS-9883/F/TAF is non-inferior to SBR if the upper bound of the 2-sided 95% confidence interval (CI) of the difference between treatment groups (GS-9883/F/TAF – SBR) in the proportion of subjects with HIV-1 RNA  $\geq 50$  copies/mL is less than 4%; ie, a margin of 4% is applied to non-inferiority assessment. The 2-sided 95% CIs will be constructed based on the exact method.

The proportion of subjects with HIV-1 RNA  $< 50$  copies/mL at Week 48 as determined by the US FDA-defined snapshot algorithm will also be summarized. The 95% CIs will be constructed in the same manner as described for the primary efficacy endpoint.

The change from baseline in CD4+ cell count at Week 48 will be summarized by treatment using descriptive statistics. The differences and the associated 95% CIs will be constructed using Analysis of Variance (ANOVA) model, including treatment (GS-9883/F/TAF vs. SBR) as a fixed effect in the model.

Adverse events and clinical laboratory assessments will be summarized using descriptive statistics.

A total of approximately 470 HIV-1 infected women, randomized in a 1:1 ratio to 2 treatment groups (approximately 235 subjects per treatment group), achieves at least 87% power to detect a non-inferiority margin of 4% difference in the percentage of subjects with HIV-1 RNA  $\geq$  50 copies/mL at Week 48 between the 2 treatment groups.

For sample size and power computation, it is assumed that both treatment groups have 2% of subjects with HIV-1 RNA  $\geq$  50 copies/mL at Week 48 (based on the historical Gilead Genvoya® (GEN) and Stribild® (STB) studies), that a non-inferiority margin is 4%, and that the significance level of the test is at a one-sided 0.025 level.

---

This study will be conducted in accordance with the guidelines of Good Clinical Practice (GCP) including archiving of essential documents.

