#### 8.5.1.2. Analysis of Primary Efficacy Endpoint

The null hypothesis is that the proportion of subjects with HIV-1 RNA  $\geq$  50 copies/mL at Week 48 in the GS-9883/F/TAF group is at least 4% higher than that in the SBR group; the alternative hypothesis is that the proportion of subjects with HIV-1 RNA  $\geq$  50 copies/mL in the GS-9883/F/TAF group is less than 4% higher than that in the SBR group.

Non-inferiority will be assessed using the conventional confidence interval (CI) approach. The point estimate of treatment difference (GS-9883/F/TAF – SBR) and the associated 2-sided 95% CI will be constructed based on the exact method.

It will be concluded that GS-9883/F/TAF is non-inferior to E/C/F/TAF if the upper bound of the 2-sided 95% CI of the difference between treatment groups (GS-9883/F/TAF – SBR) in the percentage of subjects with HIV-1 RNA  $\geq$  50 copies/mL is less than 4% (ie, a margin of 4% is applied to non-inferiority assessment).

If non-inferiority of GS-9883/F/TAF to SBR is established, the upper bound of the 95% CI will be compared to 0; if the upper bound of the 95% CI is less than 0, superiority of GS-9883/F/TAF over SBR will be established.

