1.3. Sample Size and Power

A total of approximately 470 HIV-1 infected women, randomized in a 1:1 ratio to 2 treatment groups (approximately 235 subjects per treatment group), achieves at least 87% power to detect a non-inferiority margin of 4% difference in the percentage of subjects with HIV-1 RNA ≥ 50 copies/mL at Week 48 between the 2 treatment groups.

For sample size and power computation, it is assumed that both treatment groups have 2% of subjects with HIV-1 RNA ≥ 50 copies/mL at Week 48 (based on the historical Gilead Genvoya[®] [GEN; E/C/F/TAF] and Stribild[®] [STB; E/C/F/TDF] studies), that a non-inferiority margin is 4%, and that the significance level of the test is at a one-sided 0.025 level. Sample size and power calculations were made using the statistical software package nQuery Advisor (Version 6.0).

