6. EFFICACY ANALYSES

6.1. Definition of Efficacy Endpoints

6.1.1. Primary Efficacy Endpoint

The primary efficacy endpoint is the proportion of subjects with virologic failure (HIV-1 RNA ≥ 50 copies/mL) at Week 48 as defined by the modified FDA snapshot algorithm.

The analyses of the primary efficacy endpoint were performed in the Week 48 interim analyses, and will not be repeated in the final analysis.

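### The stated power of at least 87% is not attainable at the plan's own inputs: no test holding one-sided 0.025 exceeds about 80%, and a score-ordered exact interval gives about 75%

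*Protocol*

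**What the plan says.** Protocol Section 8.8 plans about 470 women, "randomized in a 1:1 ratio to 2 treatment groups" with "approximately 235 subjects per treatment group". It states that this "achieves at least 87% power to detect a non-inferiority margin of 4% difference in percentage of subjects with HIV-1 RNA" at or above 50 copies/mL at Week 48. The inputs are 2% failures in both arms, a 4% margin and a one-sided 0.025 level. The synopsis (Statistical Methods) gives the same inputs and the same figure: "achieves at least 87% power to detect a non-inferiority margin of 4% difference in the percentage of subjects with HIV-1 RNA". SAP 1.3 repeats it: "achieves at least 87% power to detect a non-inferiority margin of 4% difference in the percentage of subjects". The SAP adds that nQuery Advisor 6.0 was used but does not name the formula. None of the three places calls the power approximate.

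For the primary analysis, Protocol Section 8.5.1.2 says that "the associated 2-sided 95% CI will be constructed based on the exact method". Non-inferiority is concluded if the upper bound is below 4%. The type of exact interval is not named. The supplied SAP covers only the final analysis of subjects on B/F/TAF. On the primary endpoint, its Section 6.1.1 says: "The analyses of the primary efficacy endpoint were performed in the Week 48 interim analyses, and will not be repeated in the final analysis".

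**The concern.** With 2% failures and 235 women per arm, the expected number of failures is 235 × 0.02 = 4.7 per arm. Large-sample power formulas for a difference in proportions are unreliable at such counts, and an exact interval is generally more conservative than a normal-approximation one. A power of 87% at these inputs therefore looked like the output of an approximation that does not describe the planned analysis.

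At stake is the sample-size justification. A reader would take the chance of missing non-inferiority with truly identical regimens to be at most 13%. If the power is overstated, that risk is understated in the synopsis, in Section 8.8 and in SAP 1.3.

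**Working it through.** **Inputs** (Protocol 8.8, synopsis, SAP 1.3): n = 235 per arm; true failure rates 2% and 2%; margin 0.04; one-sided level 0.025.

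**1. The plan's figure.** Unpooled normal approximation:

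- SE = √(2 × 0.02 × 0.98 / 235) = 0.01292
- Power = Φ(0.04 / 0.01292 − 1.96) = Φ(1.137) = 87.2%

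This matches the stated figure. That it is the origin is an inference, because SAP 1.3 names only the software.

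**2. Ceiling for any valid test.** A test that holds 0.025 over the whole null must hold it at each boundary point, where the GS-9883/F/TAF rate is a + 0.04 and the SBR rate is a. For each a, the most powerful level-0.025 test against 2%/2% is the likelihood-ratio test, randomised where needed. Its power, enumerated over all 236 × 236 outcomes, bounds every valid test. The bound is lowest at a ≈ 0.0107, where it is **80.0%**. A linear programme that maximises power subject to the level constraint gives 79.98%.

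**3. Exact unconditional intervals.** Order all outcomes on a statistic evaluated at a difference of 0.04. Take the largest rejection region whose size stays at or below 0.025 when maximised over the SBR rate from 0 to 0.96. Then compute its power at 2%/2%.

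| Ordering statistic | Power at 2%/2% |
|---|---|
| Score | **74.8%** (size 0.02499) |
| Wald | 66.9% |
| Raw difference | 0.004% |

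The raw-difference version is almost powerless because its cut-off is set by SBR rates near 50%. It needs at least 13 fewer failures on GS-9883/F/TAF than on SBR.

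**4. Approximate intervals, for comparison.**

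- Wald interval: enumerated power 85.3%, still below 87%. It does not hold its level: one-sided size is 8.9% as the SBR rate approaches 0, 5.1% at 0.5%, 3.6% at 2% and 2.9% at 5%.
- Asymptotic score interval: power 77.9%. Size is at most 2.49% for SBR rates of 0 to 20%, and 2.69% over the full null.

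As an example of the difference in decisions, with 5 SBR failures non-inferiority is met at up to 6 failures on GS-9883/F/TAF with the score-ordered exact interval, and at up to 7 with the Wald interval.

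**5. Sensitivity to the true rate, 235 per arm.**

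| True rate, both arms | Ceiling | Score-ordered exact |
|---|---|---|
| 1.0% | 94.5% | 92.6% |
| 1.5% | 87.6% | 83.6% |
| 2.0% | 80.0% | 74.8% |
| 2.5% | 72.9% | 67.6% |

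Power of 87% needs a true rate of no more than about 1.5% (ceiling) or 1.3% (score-ordered exact).

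**6. Arm size that would give 87% at 2%.** The ceiling first reaches it at 282 per arm (281 gives 86.99%). The score-ordered exact interval first reaches it at 303 per arm (86.6% at 302, 88.1% at 303).

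**7. Interim penalty.** The 0.00001 alpha penalty in Protocol Section 8.9 leaves the score-ordered power at 74.8%.

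**The case against.** The strongest reply is that nothing was miscalculated. The inputs give 87.2% under a standard formula, and Section 8.8 does not say that the figure is the power of the exact interval. It is fair to call this a mismatch between the power method and the analysis rather than a slip of arithmetic. But the text states a minimum power without qualification, and that minimum is above the attainable maximum. Even the Wald interval, which exceeds its nominal level, does not reach it.

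A second reply is that a two-sided 95% exact interval can be built by inverting a single two-sided test, which need not hold 0.025 in each tail. The score version of that interval has one-sided size 0.0253 at 235 per arm, so the 80.0% bound does not strictly cover it. For a test held only to one-sided 0.05, the bound would be 88.3%. This does not rescue the claim: Section 8.8 sets one-sided 0.025, and that interval also has 74.8% power. No exact method examined reaches 87%.

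Third, the exact method is unnamed, and the Week 48 analysis plan, which was not supplied, may name it. This stands. The 75% depends on the score ordering, which is an assumption; the 80% ceiling does not.

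Finally, overstated power cannot produce a false claim of non-inferiority, and SAP 2.2 reports the Week 48 analysis as already done, so a correction alters no enrolment. That limits the consequence. The design's stated power is still wrong on record.

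**Conclusion.** The concern holds. At 235 per arm, 2% failures in both arms, a 4% margin and one-sided 0.025, power cannot exceed about 80%, at least 7 percentage points below the stated minimum. For the score-ordered exact interval it is 74.8%, about 12 points below. The chance of missing non-inferiority with identical regimens is then at least 20% for any valid test and about 25% for that interval.

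The ceiling rests only on the plan's stated inputs and on holding 0.025 in the tail that decides non-inferiority. The 74.8% also assumes score ordering. No dropout allowance is stated in Section 8.8, and none was applied. The shortfall is tied to the assumed 2%; at 1% the score-ordered interval has 92.6% power.

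**What to change.** In the synopsis, Section 8.8 and SAP 1.3, restate the power as about 75% at 2%/2% with 235 per arm for the exact unconditional score-based interval. Add the sensitivity: 92.6% at 1%, 83.6% at 1.5% and 67.6% at 2.5%. In Section 8.5.1.2, name that interval as the exact method. If the Week 48 analysis plan names a different exact interval, cite that plan and state that interval's power instead, so that the correction describes the analysis that was run and does not choose one after the fact.

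The cost is wording in four places and a less favourable stated power. No extra participants are needed, and the margin and decision rule do not change.

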### **8.9.            Independent Data Monitoring Committee**

An external Independent Data Monitoring Committee (IDMC) will review the progress, efficacy, and safety data of this study while the study is ongoing. The committee will convene after all subjects enrolled complete Week 24 of the study or prematurely discontinue the study drug. However, Gilead will defer to the IDMC for any decision to convene earlier or more frequently. The IDMC will examine the safety results of the trial and also focus on logistical issues such as accrual, retention, quality of clinical and laboratory data, and implications of results of external studies.

No formal stopping rules will be used by the IDMC for safety outcomes. Rather, a clinical assessment will be made to determine if the nature, frequency, and severity of adverse events associated with a study regimen warrant the early termination of the study in the best interest of the participants.

An analysis for the Week 24 IDMC meeting will be conducted after the last subjects enrolled completes Week 24 of the study. For each IDMC analysis performed prior to analysis for the primary efficacy endpoint, an alpha penalty of 0.00001 will be applied for the primary analysis of the primary efficacy endpoint.

#### **8.10. Analysis Schedule**

The Week 48 analysis will be conducted after all subjects either complete their Week 48 visit or prematurely discontinue from the study drug. Final analysis will be performed after all subjects complete the study or prematurely discontinue from the study.

## **9. RESPONSIBILITIES**

### **9.1. Investigator Responsibilities**

#### **9.1.1. Good Clinical Practice**

The investigator will ensure that this study is conducted in accordance with the principles of the Declaration of Helsinki (as amended in Edinburgh, Tokyo, Venice, Hong Kong, and South Africa), International Conference on Harmonisation (ICH) guidelines, or with the laws and regulations of the country in which the research is conducted, whichever affords the greater protection to the study subject. These standards are consistent with the European Union Clinical Trials Directive 2001/20/EC and Good Clinical Practice Directive 2005/28/EC.

The investigator will ensure adherence to the basic principles of Good Clinical Practice, as outlined in 21 CFR 312, subpart D, "Responsibilities of Sponsors and Investigators," 21 CFR, part 50, 1998, and 21 CFR, part 56, 1998.

The investigator and all applicable subinvestigators will comply with 21 CFR, Part 54, 1998, providing documentation of their financial interest or arrangements with Gilead, or proprietary interests in the investigational drug under study. This documentation must be provided prior to the investigator's (and any subinvestigator's) participation in the study. The investigator and subinvestigator agree to notify Gilead of any change in reportable interests during the study and for 1 year following completion of the study. Study completion is defined as the date when the last subject completes the protocol-defined activities.

#### **9.1.2. Institutional Review Board (IRB)/Independent Ethics Committee (IEC) Review and Approval**

The investigator (or sponsor as appropriate according to local regulations) will submit this protocol, informed consent form, and any accompanying material to be provided to the subject (such as advertisements, subject information sheets, or descriptions of the study used to obtain informed consent) to an IRB/IEC. The investigator will not begin any study subject activities until approval from the IRB/IEC has been documented and provided as a letter to the investigator.

Before implementation, the investigator will submit to and receive documented approval from the IRB/IEC any modifications made to the protocol or any accompanying material to be provided to the subject after initial IRB/IEC approval, with the exception of those necessary to reduce immediate risk to study subjects.

#### **9.1.3. Informed Consent**

The investigator is responsible for obtaining written informed consent from each individual participating in this study after adequate explanation of the aims, methods, objectives, and potential hazards of the study and before undertaking any study-related procedures.

The investigator must use the most current IRB- or IEC-approved consent form for documenting written informed consent. Each informed consent (or assent as applicable) will be appropriately signed and dated by the subject or the subject's legally authorized representative and the person conducting the consent discussion, and also by an impartial witness if required by IRB or IEC or local requirements. The consent form will inform subjects about pharmacogenomic testing and sample retention, and their right to receive clinically relevant pharmacogenomic analysis results.

#### **9.1.4. Confidentiality**

The investigator must assure that subjects' anonymity will be strictly maintained and that their identities are protected from unauthorized parties. Only subject initials, date of birth, another unique identifier (as allowed by local law) and an identification code will be recorded on any form or biological sample submitted to the Sponsor, or laboratory. Laboratory specimens must be labeled in such a way as to protect subject identity while allowing the results to be recorded to the proper subject. Refer to specific laboratory instructions. NOTE: The investigator must keep a screening log showing codes, names, and addresses for all subjects screened and for all subjects enrolled in the trial. Subject data will be processed in accordance with all applicable regulations.

The investigator agrees that all information received from Gilead, including but not limited to the investigator brochure, this protocol, eCRF, the IMP, and any other study information, remain the sole and exclusive property of Gilead during the conduct of the study and thereafter. This information is not to be disclosed to any third party (except employees or agents directly involved in the conduct of the study or as required by law) without prior written consent from Gilead. The investigator further agrees to take all reasonable precautions to prevent the disclosure by any employee or agent of the study site to any third party or otherwise into the public domain.

#### **9.1.5. Study Files and Retention of Records**

The investigator must maintain adequate and accurate records to enable the conduct of the study to be fully documented and the study data to be subsequently verified. These documents should be classified into at least the following two categories: (1) investigator's study file, and (2) subject clinical source documents.

The investigator's study file will contain the protocol/amendments, CRF and query forms, IRB/IEC and governmental approval with correspondence, informed consent, drug records, staff curriculum vitae and authorization forms, and other appropriate documents and correspondence.

The required source data should include sequential notes containing at least the following information for each subject:

- Subject identification (name, date of birth, gender);
- Documentation that subject meets eligibility criteria, ie, history, physical examination, and confirmation of diagnosis (to support inclusion and exclusion criteria);
- Documentation of the reason(s) a consented subject is not enrolled

- Participation in study (including study number);
- Study discussed and date of informed consent;
- Dates of all visits;
- Documentation that protocol specific procedures were performed;
- Results of efficacy parameters, as required by the protocol;
- Start and end date (including dose regimen) of IMP, including dates of dispensing and return;
- Record of all adverse events and other safety parameters (start and end date, and including causality and severity);
- Concomitant medication (including start and end date, dose if relevant; dose changes);
- Date of study completion and reason for early discontinuation, if it occurs.

All clinical study documents must be retained by the investigator until at least 2 years or according to local laws, whichever is longer, after the last approval of a marketing application in an ICH region (ie, United States, Europe, or Japan) and until there are no pending or planned marketing applications in an ICH region; or, if no application is filed or if the application is not approved for such indication, until 2 years after the investigation is discontinued and regulatory authorities have been notified. Investigators may be required to retain documents longer if specified by regulatory requirements, by local regulations, or by an agreement with Gilead. The investigator must notify Gilead before destroying any clinical study records.

Should the investigator wish to assign the study records to another party or move them to another location, Gilead must be notified in advance.

If the investigator cannot provide for this archiving requirement at the study site for any or all of the documents, special arrangements must be made between the investigator and Gilead to store these records securely away from the site so that they can be returned sealed to the investigator in case of an inspection. When source documents are required for the continued care of the subject, appropriate copies should be made for storage away from the site.

